All screening tests, medical history and examinations will be performed only after study consent/assent where applicable is obtained. If an individual's medical chart or results diagnostic tests performed as part of an individual's medical care are going to be used for screening, written informed consent must be obtained before review of that information.

An eligibility checklist will be prepared for each participant and will later become part of the source document for participants enrolled in the trial. A unique identification number will be assigned to each study participant. A medical history will be taken. Concomitant medications will be documented. Physical examination (including Blantyre coma score (BCS)) and laboratory

screening tests will include: hemoglobin, platelets, white blood cell (WBC) count, neutrophil count; serum lactate, bicarbonate, blood urea nitrogen (BUN), calcium, creatinine, glucose, alanine aminotransferase (ALT), aspartate aminotransferase (AST), total and direct bilirubin, sodium, and potassium; and urinalysis. Laboratory testing will be performed at the Lancet laboratory at the study site and at a local reference laboratory if needed. Results obtained within 24 hours prior to enrollment can be included as baseline labs and would satisfy both screening and enrollment/baseline labs. A thick and thin blood smear will be performed for estimation of parasite density. A dried blood spot specimen will be collected for artemisinin resistance assessment. A blood specimen will be collected in a PAXgene tube for *P. falciparum* gene expression analysis. Recruitment will continue over a single malaria transmission season until up to 100 eligible participants have fulfilled all the inclusion criteria and none of the exclusion criteria.

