8 STUDY PROCEDURES/EVALUATIONS

8.1 Daily Study Procedures

Screening (may take place over more than one visit) up to 24 hours before enrollment

- Written assent for children \geq 8 years as applicable
- Informed consent obtained from the parent
- Check of inclusion and exclusion criteria
- Participant identification number assigned
- Demographics and medical history of participant
- Concomitant medication documentation
- Physical examination and vital signs (pulse, respiratory rate, blood pressure, axillary temperature)
- Document height and weight
- BCS
- Urinalysis
- Collect 8.25 mL venous blood sample for:
 - Hematology: hemoglobin, platelets, WBC count, neutrophil count
 - Biochemistry: serum creatinine, AST, ALT, total and direct bilirubin, bicarbonate, lactate, sodium, potassium, glucose, BUN, calcium
 - *P. falciparum* parasite quantification
 - Artemisinin resistance
 - Population PK study per sampling plan specified in Section 8.3.1
 - *P. falciparum* mRNA collection using PAXgene tube

Day 1 Enrollment

- Physical examination and vital signs (pulse, respiratory rate, blood pressure, axillary temperature every 6 hours until 6 hours post-parasite clearance)
- Urinalysis

- An IV cannula will be inserted for administration of study drugs and for PK blood sampling and blood draws.
 - Collect venous blood samples for population PK study per sampling plan specified in Section 8.3.1
 - Administration of IV artesunate dose in accordance with WHO and Uganda guidelines
- Collect 11.5 mL venous blood sample for:
 - Hematology: hemoglobin, platelets, WBC count, neutrophil count (at least 12 hours after initial screening collection)
 - Biochemistry: serum creatinine, AST, ALT, total and direct bilirubin, serum bicarbonate, lactate, sodium, potassium, glucose, BUN, calcium (at least 12 hours after initial screening collection)
 - Population PK study per sampling plan specified in Section 8.3.1
 - *P. falciparum* parasite quantification
- Concomitant medication review
- BCS

Day 2 Follow-up

- Physical examination and vital signs (pulse, respiratory rate, blood pressure, axillary temperature)
- Administration of IV artesunate dose or ACT in accordance with WHO and Uganda guidelines
- Urinalysis
- Collect 3.5 mL venous blood sample for:
 - Hematology: hemoglobin, platelets, WBC count, neutrophil count
 - Biochemistry: serum creatinine, AST, ALT, total and direct bilirubin, serum bicarbonate, lactate, sodium, potassium, glucose, BUN, calcium

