3.3. Study Definitions and Derived Variables

Severe Malaria

Severe malaria is defined as presence or history of fever plus a positive blood film for *P. falciparum* malaria with at least one of the following symptoms and signs:

- Repeated convulsions: More than two episodes within 24 h
- Impaired consciousness: A Blantyre coma score < 3 in children
- Coma
- Hyperpyrexia: Axillary temperature $\geq 40^{\circ}\text{C}$
- Respiratory distress: Acidotic breathing
- Inability to tolerate oral therapy and vomiting all oral intake
- Circulatory collapse or shock: Systolic blood pressure < 50 mmHg in children
- Spontaneous bleeding
- Hemoglobinuria: Hemoglobinuria presents as tea colored urine
- Jaundice
- Prostration: Extreme weakness so that the person is unable to sit, stand or walk without assistance
- Severe normocytic anaemia: Hemoglobin concentration < 5 g/dL
- Hypoglycemia: Blood or plasma glucose < 2.2 mmol/L (< 40 mg/dL)
- Renal impairment: Plasma or serum creatinine > 265 $\mu\text{mol/L}$
- Hyperparasitemia: *P. falciparum* parasitemia > 10%

Whether participants meet this definition of severe malaria will be evaluated in the process of determining enrollment eligibility. Participant history of fever, indication of positive blood film for *P. falciparum* malaria, and the presence of additional assessed symptoms and signs of severe malaria will be documented in the appropriate electronic case report form (eCRF). Only one additional sign or symptom of severe malaria must be present along with history of fever and positive blood film for *P. falciparum* malaria for a participant to meet the definition of severe malaria. Once a participant meets the definition of severe malaria, investigators may opt not to assess the participant for additional signs and symptoms. Reported symptoms and signs of severe malaria at enrollment will be summarized in [Table 6](#).

Baseline

Baseline values of primary outcome measures of physiological dysfunction, laboratory parameters, and vital signs will be defined as the most recent measurement before first dose of IV artesunate. If these measurements are not collected before first dose, such as for participants who received IV artesunate before enrollment, baseline values will be defined as either the screening measurement or the earliest measurement after first dose of IV artesunate, whichever is closest to time of first dose of IV artesunate.

Weight-for-Age and Height-for-Age Z-Scores

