4.5. Pharmacodynamics, Pharmacokinetics, Immunogenicity, and Safety Variables

4.5.1. Pharmacodynamics Variables

The primary PD outcome response variables are temperature, blood pressure, serum lactate, serum bicarbonate, serum glucose, total and direct bilirubin, hemoglobin, creatinine, and BCS.

BCS is an ordinal scale designed to assess malarial coma in children. Eye movement, best motor response, and best verbal response are assessed and scored according to the evaluation criteria presented in the table below. The BCS is then calculated as the sum of the scores for these three assessments, with possible values of 0, 1, 2, 3, 4, or 5. Lower BCS values are indicative of impaired consciousness.

Assessment	Evaluation Criteria	Score
Eye Movement	Watches or follows – 1 Fails to watch or follow – 0	0 or 1
Best Motor Response	Localizes painful stimulus – 2 Withdraws limb from painful stimulus – 1 No response or inappropriate response – 0	0, 1, or 2
Best Verbal Response	Cries appropriately with pain, or, if verbal, speaks – 2 Moan or abnormal cry with pain – 1 No vocal response to pain – 0	0, 1, or 2
Total Score		0, 1, 2, 3, 4, or 5

Primary PD outcome response variables will be recorded at least daily for each patient while hospitalized and at scheduled follow-up visits according to the schedule in [Table 2](#).

Dates and times of hospital admittance and discharge for each participant will be collected on the appropriate eCRF for calculation of time to hospital discharge. Time to hospital discharge is defined as the time in days from initial participant admission to the time of first discharge. Time to hospital discharge will be calculated using the actual dates and times of initial participant admission and first discharge and will be rounded to the nearest tenths place.

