6.3.3. Pharmacodynamic Analysis Population

The PD Analysis Population will include all participants meeting the definition of severe malaria at enrollment for which exposure parameters can be estimated from the final population PK model and for which post-baseline response data are available.

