6.5. Missing Data

Every effort will be made to minimize missing data and collect all outcome measures specified in this protocol. Participants who discontinue treatment will be followed after treatment discontinuation for collection of all scheduled follow-up data with their consent.

Missing dose data (dosing time, or dosing date) will be imputed to maximize the inclusion of observations subsequent to doses with missing information. Missing dosing time will be imputed if the dose date and amount are available:

- If dosing times are missing, the pre-dose sample time combined with the dose number and dosing timeline will be used to determine the pre-study and on-study dosing times.
- Dosing time will be imputed as the mean of the time from pre-dose draw to dosing for those not missing the given sampling window.

Missing covariate data for analyses that incorporate confounding covariate variables will be handled in the following manner. The covariate will be excluded from the analysis if more than 20% of the covariate values are missing. Baseline individual covariates, including sex and weight group, will be determined from the Day 1 visit. If an individual's baseline covariate is missing at the Day 1 visit, the baseline covariate value will be taken from either the pre-study (screening) visit or from the earliest post-dose visit, whichever is closest to the baseline visit. Receipt of IV artesunate or artemisinin-based therapy before enrollment will be determined from treatment administration records with dates and times before the first on-study dose and/or concomitant medication records with dates up to the Day 1 visit. Receipt of oral ACT, which has planned collection occurring after baseline, will be determined from all visits up to and including the visit at which the analysis timepoint occurs.

No imputation will be performed for missing primary or secondary PD outcome response variables. Rather, only participants in the PD Analysis Population with the PD outcome response variable measured at the timepoint of interest will be included in PD analyses of that PD outcome response variable measured at the timepoint of interest.

Please refer to the Pharmacometrics Analysis Plan for details pertaining to methods for missing concentration data and other missing data that would affect the PK analysis.

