8.1. Primary Pharmacodynamics Analysis

The primary PD analysis will be performed to assess the relationship between DHA PK exposure parameters, including AUC_{0-12} , C_{max} , $t_{1/2}$, and T_{max} , and markers of physiological dysfunction known to be associated with severe malaria. These markers of physiological dysfunction measured at planned follow-up times will be the primary outcome response variables, and will include temperature, systolic and diastolic blood pressure, serum lactate, serum bicarbonate, serum glucose, BCS, total and direct bilirubin, hemoglobin, and creatinine. Values of AUC_{0-12} , C_{max} , $t_{1/2}$, and T_{max} for each participant will be treated as fixed in all PD analyses. Details of the calculation of AUC_{0-12} , C_{max} , T_{max} , and $t_{1/2}$ can be found in the Pharmacometrics Analysis Plan.

Planned follow-up times at which the relationships between each marker of physiological dysfunction and exposure parameter will be assessed include:

- Approximately 24 hours post-first dose, for which the most recent measurement of each physiological dysfunction variable before 24 hours post-first dose will be utilized as the response;
- Approximately 48 hours post-first dose, for which the most recent measurement of each physiological dysfunction variable before 48 hours post-first dose will be utilized as the response;
- Time of completion of the final planned dose of IV artesunate, for which the first measurement of each physiological dysfunction variable after completion of the final planned dose of IV artesunate will be utilized as the response; and
- Time of first hospital discharge, for which the most recent measurement of each physiological dysfunction variable before the time of first hospital discharge will be used as the response.

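### The 24 h and 48 h primary responses have no earliest limit, so a laboratory or coma-score response can be half a day or a day old, and at 24 h it can be the pre-treatment baseline itself

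*SAP*

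**What the plan says.** SAP 8.1 names four timepoints for the primary analysis. For the first, "the most recent measurement of each physiological dysfunction variable before 24 hours post-first dose will be utilized as the response"; for the second, "the most recent measurement of each physiological dysfunction variable before 48 hours post-first dose will be utilized as the response". No earliest time is given, nothing after the hour is eligible, and nothing says the value must follow the dose.

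SAP 3.3 says baseline "will be defined as the most recent measurement before first dose of IV artesunate". Where no pre-dose value exists, baseline is the screening value or the earliest post-dose value, whichever is closer to the first dose.

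On frequency, SAP 4.5.1 says the primary response variables are "recorded at least daily for each patient while hospitalized". Vital signs are denser, at about every 6 h until 6 h after parasite clearance (SAP 9.7). In Protocol 8.1 the Day 1 hematology and biochemistry are due "at least 12 hours after initial screening collection". Protocol 7.1 adds: "Results obtained within 24 hours prior to enrollment can be included as baseline labs and would satisfy both screening and enrollment/baseline labs". The Day 2 sample in Protocol 8.1 covers hematology, biochemistry and the parasite count together. The 24 h smear has a window of 22 to 26 h (Protocol 8.3.1), but the laboratory markers and BCS have none.

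**The concern.** The rule can label as a 24 h response a value that was not measured near 24 h, or was measured before any drug was given. In that last case SAP 3.3 and SAP 8.1 select the same record. It enters the model as the outcome and as the baseline term, and in Table 13 the child shows a change of exactly 0 at 24 h after the first dose. Meanwhile a draw taken minutes after the target hour is not eligible for that timepoint.

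These responses carry the primary exposure-response tests, in a study meant to inform dosing (SAP 2.1). Stale or pre-treatment values would dilute a real exposure effect, and the power figures in SAP Table 3 make no allowance for that.

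**Working it through.** **1. The plan's own power figure.** Inputs from SAP 5 and Table 3: 176 tests, R² = 0.2, 5% non-null (176 × 0.05 = 8.8, taken as 9), N = 75, Benjamini-Hochberg at 0.05. A simulation with simple linear regression, independent two-sided tests and 5000 runs gives 0.852; Table 3 states 0.85. All 25 cells of Table 3 that were checked agree within 2 points.

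**2. What the rule selects.**

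| Case | Eligible draws | Response used |
|---|---|---|
| Screened at dosing, Day 1 draw 12 h later, Day 2 draw at 24 h 05 min | 0 h, 12 h | the 12 h value |
| Screened 12 h before dosing, Day 1 draw 12 h after screening (at or before dosing), Day 2 draw at 24 h 05 min | pre-dose only | the baseline |
| No separate Day 1 draw, Day 2 draw at 24 h 05 min | pre-dose only | the baseline |
| Day 2 draw near 24 h, Day 3 draw at 48 h 05 min | up to Day 2 | the Day 2 value, about 24 h before target |

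The SAP itself provides for an absent Day 1 draw: the implementation note to Table 33 says what to do if no participant has post-baseline Day 1 chemistry.

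**3. Possible safeguards.** SAP 6.5 says "only participants in the PD Analysis Population with the PD outcome response variable measured at the timepoint of interest will be included in PD analyses", but the look-back rule is the only definition of what counts as the timepoint. SAP 6.3.3 admits children "for which post-baseline response data are available", a condition on the child and not on each marker and timepoint. The subset without prior artemisinin therapy uses the same response rule. Actual measurement time is always in the BCS model, is optional in the linear and polynomial models, and is not in the Emax equation. Adjusting for time helps with a 12 h value, but it cannot turn a pre-dose value into a response to drug.

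**4. Tests exposed.** Seven laboratory markers (lactate, bicarbonate, glucose, total bilirubin, direct bilirubin, hemoglobin, creatinine) plus BCS make 8. Then 8 × 4 exposures × 2 timepoints = 64 of 176, of which 8 × 4 = 32 are at 24 h.

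**5. How many Day 2 draws might be ineligible.** The documents do not say. If laboratory draws were uniform over the smear window of 22 to 26 h (an assumption), the share at or after 24 h is (26 − 24)/(26 − 22) = 50%. Centred 1 h earlier it is (25 − 24)/4 = 25%; centred 1 h later, (27 − 24)/4 = 75%.

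**6. Illustration of the power loss.** Suppose a share f of responses in every non-null test is a baseline value, unrelated to exposure and with the same variance. Then effective R² = 0.2 × (1 − f)². With 176 tests and 5% non-null:

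| f | Effective R² | Power, N=75 | Power, N=100 |
|---|---|---|---|
| 0 | 0.200 | 0.85 | 0.96 |
| 0.10 | 0.162 | 0.69 | 0.87 |
| 0.25 | 0.1125 | 0.40 | 0.61 |
| 0.50 | 0.050 | 0.07 | 0.13 |

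Baseline substitution needs both a late Day 2 draw and no post-dose Day 1 draw. With 50% of draws late and the two events independent, f = 0.10 requires 0.10/0.50 = 20% of children without a post-dose Day 1 draw, and f = 0.25 requires 0.25/0.50 = 50%. For a given f the table overstates the harm, because it applies f to every non-null test and not all tests are exposed. Like Table 3, it has no baseline term in the model.

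**The case against.** The rule is prespecified and reproducible, and the study calls itself hypothesis-generating. The likely effect is dilution, not false positives. Stopping before 24 h also has a logic: the third dose and the assessment for oral therapy fall at 24 h, and the cut-off keeps the response ahead of both. Protocol 8.1 lists a Day 1 draw and Protocol 7.1 does not expressly waive it, so the baseline case needs two events together. SAP 8.1 speaks of planned follow-up times and Table 13 gives baseline its own row, which suggests the authors had a later value in mind.

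Most of this stands as a limit on size. It does not repair the rule: an earliest limit and a post-dose condition are compatible with a cut-off at 24 h, and intent that is not written down will not govern the derivation.

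Some stronger readings are tempting, and the documents do not support them:

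- A reader might infer that all 11 × 4 × 2 = 88 tests at these timepoints are exposed. Temperature and both blood pressures are taken about every 6 h until 6 h after clearance, so their look-back is normally 6 h or less while that schedule runs.
- A reader might infer that baseline is equally likely to be the response at 48 h. That would need every intervening value to be missing.
- A reader might infer that a late draw is lost. It is lost only to that timepoint; it can still serve the 48 h look-back or the timepoint after the final planned dose.

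**Conclusion.** The derivation is wrong as written for the laboratory markers and BCS. Nothing in the SAP stops the 24 h response from being a value about 12 h old or the baseline record, and at 48 h the usual fallback is about a day old. The reach is 64 of 176 primary tests; the baseline case is mainly a matter for the 32 at 24 h. Actual measurement time in the models compensates only in part.

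The frequency cannot be known from the documents. The fall from 0.85 to about 0.69 or 0.40 shows sensitivity to shares of 10% and 25%; it is not an estimate of what will happen. A reader might want a firmer figure for lost power or a flattened slope. That would need a rate of marker recovery and a distribution of laboratory draw times, and the documents give neither.

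**What to change.** In SAP 8.1, require the 24 h and 48 h responses to be taken after the first dose, to be a different record from the SAP 3.3 baseline, and to lie within a stated window around the target hour. Otherwise the response is missing at that timepoint. Both of the first two conditions are needed, because SAP 3.3 lets a post-dose value serve as baseline when no pre-dose value exists.

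Set the window before database lock from the distribution of draw times alone, without looking at responses or exposures. No width for the laboratory markers has a source in the documents. State whether values after the hour are eligible, given the dose and oral-therapy assessment due at 24 h: a window that spans the hour mixes values from before and after them, and SAP 8.1 limits the oral-therapy covariate to the discharge timepoint. Apply the rule to Tables 13 to 18 and report the actual measurement times used.

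The cost is SAP wording and derivation code, with no new data. The downside is that some children become missing at a timepoint instead of carrying an old value. This may be more than a few: if draws were at one fixed clock hour and first doses were spread evenly over the day, a window w hours wide would catch w/24 of the children. A 12 h window would catch 12/24 = 50%, unless a Day 1 draw also fell inside it. The draw times should therefore be examined before the width is fixed.

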Sample sizes considered in these simulations included 100 or 80 participants. These original simulation results indicate that the target sample size of 100 participants provides >90% power for detecting simple linear relationships for 24 or 48 tests with an underlying R^2 of at least 0.2, if the proportion of non-null relationships among those tested is at least 5%. If at least 80 participants complete follow-up for the primary outcome measure, power for the same scenario is approximately 88%.

However, at the end of the planned enrollment period of 6 months, only 46 participants had been enrolled in the study. Further simulations were performed under the same settings described above with smaller sample sizes considered. These results are also provided in Table 3. These simulation results indicate that if at least 70 participants complete follow-up for the primary outcome measure, power for detecting simple linear relationships for 24 or 48 tests with an underlying R^2 of at least 0.2, if the proportion of non-null relationships among those tested is at least 5%, is $\geq 80\%$.

Additionally, given that there are eleven markers of physiological dysfunction, four exposure parameters, and four timepoints (see Section 8.1) of interest, the total number of possible hypothesis tests for all of these relationships is 176. Further simulations were performed under the same settings described above with 176 tests and sample sizes of 75, 80, or 90 participants considered. These results are also provided in Table 3. These simulation results indicate that if at least 75 participants complete follow-up for the primary outcome

measure, power for detecting simple linear relationships for 176 tests with an underlying R^2 of at least 0.2, if the proportion of non-null relationships among those tested is at least 5%, is greater than 80%.

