6.8. Multiple Comparisons/Multiplicity

The primary analysis involves assessing multiple exposure-response relationships measured at multiple timepoints, which can be framed as a series of hypothesis tests to evaluate these potential relationships. To accommodate the multiple hypothesis tests in the primary analysis, the set of p-values corresponding to tests of the effect of exposure on response at each timepoint will be adjusted using the Benjamini-Hochberg procedure to preserve the false discovery rate for the primary outcome at 0.05. There are no adjustments for multiple comparisons planned for secondary or exploratory analyses.

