Exploratory scatterplots of each continuous primary outcome response variable will be presented by exposure parameter and timepoint beginning in [Figure 2](#) and continuing through [Figure 11](#) for the PD Analysis Population. Exploratory box plots of BCS will be presented by exposure parameter and timepoint in [Figure 12](#). Summary statistics for each continuous marker of physiological dysfunction and its change from baseline will also be presented by parameter and timepoint in [Table 13](#) for participants in the PD Analysis Population and in [Table 14](#) for the subset of the PD Analysis Population with no IV artesunate or other artemisinin-based therapy before enrollment. Proportions of participants with each BCS value will be presented by timepoint in [Table 15](#) for participants in the PD Analysis Population and in [Table 16](#) for the subset of the PD Analysis Population with no IV artesunate or other artemisinin-based therapy before enrollment.

Regression models will be fit to characterize the relationship between each primary outcome response and each exposure parameter at each of the above timepoints, controlling for covariates (given in Section 6.4). Note that receipt of oral ACT will only be considered for inclusion in analyses of the primary outcome

response variables at time of first hospital discharge. Exploratory boxplots of each continuous primary outcome response variable will be presented by covariate and timepoint beginning in [Figure 13](#) and continuing through [Figure 22](#). Exploratory stacked bar charts of BCS will be presented by covariate and timepoint in [Figure 23](#). These exploratory plots, presented for the PD Analysis Population, will be used to inform what subset of covariates will be included in each model.

Proportional odds mixed effects models will be used to assess the relationship between each exposure parameter and ordinal BCS at each timepoint. The proportional odds mixed effect model for BCS at any one of the four timepoints considered is defined as follows:

$$\text{logit}\{\tau_k(P_i, t_i, BCS_{0,i}, X_i)\} = \alpha_k + \beta_1 P_i + \beta_2 t_i + \eta^T X_i + BCS_{0,i} + b_i.$$

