where E_i represents the given response outcome measure for the i th participant at the given timepoint, $E_{0,i}$ is the baseline response outcome measure for participant i , P_i is the exposure parameter value for participant i , a is the highest order exponent included in the model with its selection informed by exploratory data plots, X_i are the values of the additional covariates included in the model, and e_i are the measurement errors for participant i . These measurement errors are assumed to be independent and normally distributed with mean zero and nonzero variance. Again, in addition to the covariates listed in Section 6.4, actual time of response measurement post-first dose will also be considered for inclusion in the model. Estimated log-likelihood statistics or other model fit statistics may be used to assist in covariate selection for linear or polynomial models.

If linear models are fit for a primary outcome effect, the following pseudocode will be used for model fitting and to extract p-values for the exposure model parameter.

```
/* Polynomial model fit and output p-values */
data dataset; set dataset;
```

```

*exposure^j from 2 up to a will be calculated;
exposurea=exposure**a;
exposurea_1=exposure** (a-1);...
run;
proc glm data=dataset(where=(population=p and response=r));
*catvar = any categorical covariates included in the model;
*refvalues = the value(s) to be used as the reference level for categorical
covariate(s);
class catvar(ref=refvalues);
*exposure... exposurea: exposure raised to the powers 1 up to a will be included as
covariates in the model;
*baseresp = response at baseline;
*othercovars = any other covariates (including those specified in the class statement)
included in the model;
model resp = baseresp exposure... exposurea othercovars / noint ss3;
by timepoint;
ods output ModelAnova=tests3;
run;
data tests3; set tests3(where=(source='exposurea'));
rename ProbF=pval;
run;

```

Model assumptions, including normality of participant-specific measurement errors, will be assessed via exploratory scatterplots and residual plots, which will also inform whether a log-transformation of the response variable may be necessary. In the event that model assumptions are not met, additional models or transformations of the response variables will be assessed, and any changes from the analyses described in this SAP will be fully described in the interim CSR.

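### Polynomial order is chosen from response-by-exposure plots and only the top coefficient is then tested, so the 0.05 false discovery rate claimed for the primary analysis is not assured

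*SAP*

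**What the plan says.** SAP 8.1 fits a separate model for each marker, exposure parameter and timepoint. SAP 5 states that "the total number of possible hypothesis tests for all of these relationships is 176", that is 11 × 4 × 4. Ten markers are continuous (10 × 4 × 4 = 160 tests). The Blantyre Coma Score (BCS) supplies the other 16, under a fixed proportional-odds form.

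For the continuous markers, an Emax model comes first. If its assumptions look doubtful, a linear or polynomial model is considered in the light of the response-by-exposure scatterplots. The polynomial order *a* "is the highest order exponent included in the model with its selection informed by exploratory data plots". No maximum order and no decision rule are given. For a polynomial, the null hypothesis is β_a = 0 alone. The pseudocode keeps only that p-value, and Table 17 reports only that coefficient.

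A log transformation of the response is judged from the same scatterplots and from residual plots. Covariates are a subset of the SAP 6.4 list, for which plots of response by covariate "will be used to inform what subset of covariates will be included in each model". For linear and polynomial models, "Estimated log-likelihood statistics or other model fit statistics may be used to assist in covariate selection".

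Under SAP 6.8 the resulting set of p-values "will be adjusted using the Benjamini-Hochberg procedure to preserve the false discovery rate for the primary outcome at 0.05", and Table 17 flags those that pass. SAP 5 gives "power for detecting simple linear relationships for 176 tests with an underlying R^2 of at least 0.2", assuming that at least 5% of the relationships are real. Protocol 11.3.5 said the SAP would name pre-specified covariates and define each response, including possible transformations.

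**The concern.** Benjamini-Hochberg controls the FDR only if each p-value from a true null behaves as a p-value should: below 0.05 at most 5% of the time, below 0.001 at most 0.1% of the time, and so on. An order that is kept because the curve appears to fit, and whose top term is then tested on the same data, has been selected for a small p-value.

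There is also a cost in power. If the true relation is a straight line and a curve is chosen, the reported test asks whether there is curvature. It no longer asks whether response changes with exposure.

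SAP 2.1 says the study is meant to inform dosing regimens. The flagged entries of Table 17 are what readers will take from it, and the 0.05 attached to them should mean what it says.

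**Working it through.** **Inputs from the SAP.** m = 176 tests and q = 0.05. The non-null share is 5%: 0.05 × 176 = 8.8, rounded to 9, leaving m0 = 167 true nulls. R² = 0.2. N = 80 is one of the Table 3 sizes.

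**Assumptions.** Tests are two-sided and independent; the SAP states neither. The selection runs use a baseline value and four binary covariates.

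**1. Reproduce Table 3.** This used the slope test in a linear model fixed in advance, with 5,000 replicates and Benjamini-Hochberg at 0.05.

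| N (176 tests, 5% non-null) | SAP power | Recomputed power | Realised FDR |
|---|---|---|---|
| 90 | 0.93 | 0.929 | 0.048 |
| 80 | 0.88 | 0.883 | 0.045 |
| 75 | 0.85 | 0.853 | 0.047 |

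With valid p-values the expected FDR is q × m0/m = 0.05 × 167/176 = 0.047, which agrees. The other Table 3 cells that were inspected matched within 2 points; four cells (24 tests, 10% non-null) were not inspected. Table 3 is therefore right for a test that is fixed in advance.

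**2. Choose the order from the data, then test only the top coefficient (N = 80).** The SAP defines no rule, so AIC and BIC stand in for the visual choice, and every test is put through the selection.

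| Rule | Null rejections at 0.05 | Null rejections at 0.001 | FDR, 176 tests | Average power, linear effect |
|---|---|---|---|---|
| Fixed linear model | 0.049 | 0.0012 | 0.051 | 0.87 |
| Orders 1-2, AIC | 0.091 | 0.0020 | 0.100 | 0.71 |
| Orders 1-3, AIC | 0.129 | 0.0027 | 0.129 | 0.65 |
| Orders 1-3, BIC | 0.104 | 0.0030 | 0.143 | 0.84 |

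A hand check supports the FDR column. Benjamini-Hochberg works at small cut-offs; for 9 rejections the cut-off is 0.05 × 9/176 = 0.0026. If null p-values fall below such cut-offs *c* times too often, FDR is roughly c × 0.0474. Taking *c* from the 0.001 column:
- orders 1-2, AIC: 2.0 × 0.0474 = 0.095
- orders 1-3, AIC: 2.7 × 0.0474 = 0.128
- orders 1-3, BIC: 3.0 × 0.0474 = 0.142

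**3. Repeat runs.**
- At N = 75 and 80, with normal and lognormal exposure and 6,000 null datasets per cell, AIC gave 9.1-9.6% rejections (orders 1-2) and 12.8-13.3% (orders 1-3). A fixed linear test gave 4.5-5.2%. A joint F-test of all exposure terms at a fixed order gave 4.6-5.2%.
- A further AIC run at N = 80 gave 8.1% and 12.5%, FDR of about 0.08-0.12, and power falling from about 0.90 to 0.69-0.76.

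**4. The other two data-driven choices, each taken alone (N = 80).**

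| Choice | Per-test error | Per-test error, covariate tied to exposure and response | FDR |
|---|---|---|---|
| Covariates by association with response | 0.050 | 0.051-0.059 | 0.049-0.050 |
| Covariates by AIC | 0.057 | 0.070 | 0.062 |
| Transformation by residual shape | 0.048-0.056 | – | 0.055 |

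**Not examined:** the Emax test of EC50 = 0, and correlation among the 176 tests.

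**The case against.** The sponsor has a fair case on several counts.

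- **The study is declared exploratory, and Table 19 will disclose every model, covariate set and transformation.** Both are true and bear on severity. Neither restores the error rate. An exploratory label would justify dropping the FDR claim, but the SAP makes the claim and flags results by it.
- **Emax comes first, so few tests may reach a polynomial.** This stands. The simulated sizes put every test through order selection, so they describe a high-use scenario.
- **AIC is not the SAP's rule for order.** This also stands. The SAP assigns fit statistics to covariate selection and to Emax model selection; order rests on plots. An analyst who rarely departs from a straight line would cause less inflation.
- **Covariates are handled.** Largely so. The four main candidates are named in SAP 6.4, the linear and polynomial pseudocode already includes the baseline value, and a sensitivity analysis removes children with prior artemisinin therapy.

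A reader might infer from the covariate wording that covariate choice is what breaks the error rate. It is not: those plots show response by covariate and do not involve exposure, and step 4 finds about 5-7% per-test error from covariate choice.

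**Conclusion.** The point holds in a limited form. For the continuous markers, choosing family and order from response-by-exposure plots and then testing only β_a means that FDR control at 0.05 is not assured, and the Table 3 power does not apply to that procedure.

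The size is conditional on an assumed rule. With order chosen by AIC in every continuous test at N of about 80, per-test error is about 8-13%, FDR is about 0.08-0.13 (0.14 with BIC), and average power for a linear effect falls from 0.87-0.90 to 0.65-0.76 (0.84 with BIC). Covariate choice is a minor contributor and transformation choice a negligible one.

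Three stronger readings go beyond the documents.
- That the FDR certainly fails: the visual rule is undefined, so neither failure nor control can be shown.
- That all 176 tests are affected: the 16 BCS tests involve no order choice.
- That 160 × 0.129 = 21 false findings would be reported against 160 × 0.05 = 8: those are counts of unadjusted p-values below 0.05, not of results that pass Benjamini-Hochberg.

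**What to change.** Before the data are analysed, amend SAP 8.1 and 6.8 as follows.

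- Name one exposure test per marker, exposure parameter and timepoint to enter Benjamini-Hochberg. For continuous markers this should be either the slope in a linear model, which matches the basis of Table 3, or a joint test of all exposure terms at one fixed order. β_a alone, after order selection, should never be the entry.
- Use one covariate set in every primary model: baseline marker, sex, weight group, prior artemisinin therapy and antimalarial concomitant medication. This delivers the pre-specification promised in Protocol 11.3.5 and keeps weight group, which sets the mg/kg dose, in every model.
- Fix the response transformation for each marker.
- Report data-chosen Emax and polynomial fits as descriptive displays, without significance flags.

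The cost is SAP wording and a few degrees of freedom per model. The linear test loses some power for curved relations; the joint test loses some for linear ones. If the joint test is chosen, the power simulation should be rerun for it.
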